Section 8.4.1	
Per protocol, procedures Procedures at each visit should generally be, but are not required to be, performed in the order listed in Table 3 (Schedule of Visits and Procedures). Every effort should be made to follow this order to ensure that the performance of particular procedures do not affect the results of subsequent assessments. However, should Should the site need to reorder some of the procedures to fit into their standard practices, the following procedures MUST be completed in the order shown below due to potential impact on the subsequent assessments:
	For clarification.
Section 8.4.1	
Removed blood sampling for pharmacokinetic analysis.
	To eliminate redundancy.

Section	Revision	Rationale
Section 8.4.2	Per protocol, procedures Procedures at each visit should generally be, but are not required to be, performed in the order listed in Table 4 (Schedule of Visits and Procedures). Every effort should be made to follow this order to ensure that the performance of particular procedures do not affect the results of subsequent assessments. However, should Should the site need to reorder some of the procedures to fit into their standard practices, the following procedures MUST be completed in the order shown below due to the potential impact on the subsequent assessments:	For clarification.
Sections 8.4.2.8, 8.4.2.9, 8.4.2.10, and 8.4.2.11	Added (– Retreated Patients Only) to the section headings.	For clarification.
Section 8.12.1	Deleted “(ie, pharmacodynamics).”	For clarification.
Section 9.5.2	For stage 1, cohort 1, a kit will contain [REDACTED] [REDACTED] for stage 1, cohorts 2 to 6D, a kit will [REDACTED] [REDACTED] [REDACTED] for stage 2, treatment group 1, a kit will [REDACTED] [REDACTED] for stage 2, treatment groups 2 and 3, a kit will contain [REDACTED] [REDACTED]	For clarification.
Section 10	Added the following reference: Neoral® (package insert). East Hanover, NJ: Novartis Pharmaceutical Corporation; 2015.	For completeness.
Section 11.1.16	Conjunctival epithelial cells will be collected via impression cytology from each eye for efficacy pharmacodynamic analyses from 2 locations around the superior–temporal bulbar conjunctiva.	For clarification.
Section 11.2	Deleted the brief description of the [REDACTED].	To allow reference to more detail within the [REDACTED].

ALLERGAN

Protocol 192371-024 Amendment 6

Date (DD/MMM/YYYY)/Time (PT)

19-Jan-2017 07:56 GMT-080

Signed by:

2.2 List of Figures

Figure 4-1	Stage 1 Study Flow – Dose Escalation In Patients With Moderate To Severe Dry Eye Disease.....	10
------------	---	----

3. List of Abbreviations and Definition of Terms

Table 3-1 Abbreviations and Definitions of Terms

Abbreviation/Term	Definition
AE	adverse event
BCVA	best-corrected visual acuity
CFB	change from baseline
DDE	Drug Dictionary Enhanced
█	█
eCRF	electronic case report form
F1	█
F2	█
IOP	intraocular pressure
MedDRA	Medical Dictionary for Regulatory Activities
mITT	modified intent-to-treat
OSDI	Ocular Surface Disease Index
PK	pharmacokinetic
PT	preferred term
SAE	serious adverse event
SAP	statistical analysis plan
SOC	system organ class
TEAE	treatment-emergent adverse event
TBUT	tear film break-up time
VAS	visual analog scale
WHO	World Health Organization

4. Introduction

This statistical analysis plan (SAP) details comprehensive, technical specifications of the statistical analyses of the safety, exploratory efficacy, and health outcomes data outlined and/or specified in Protocol 192371-024 Amendment 6, dated 19 Jan 2017. Study 192371-024 is a 2-stage, Phase 2 study. A final database lock will occur after the completion of stage 2. Separate analysis plans will be prepared for the analysis of each stage. This document is the analysis plan for stage 1. Specifications of tables, figures, and data listings are contained in a separate document. The SAP for pharmacokinetic (PK) data will be prepared separately.

This document is organized into 3 main sections as follows:

1. Study overview
2. Statistical methodology and study endpoints
3. Data handling and analysis conventions

4.1 Study Design Summary

This study is a multicenter, randomized, investigator-masked, 24-week evaluation of the safety, exploratory efficacy, and pharmacokinetics of [REDACTED] RESTASIS® X in patients with moderate to severe dry eye disease. The study is being conducted in 2 stages.

Stage 1: Single-dose, paired-eye comparison, dose escalation, vehicle-controlled, followed by retreatment (Cohorts 6C and 6D).

Stage 1 will evaluate the safety and ocular and systemic pharmacokinetics of F1 [REDACTED] and F2 [REDACTED]. [REDACTED]

[REDACTED]

[REDACTED]

[REDACTED]

[REDACTED]

[REDACTED]

[REDACTED]

[REDACTED]

[REDACTED]

[REDACTED]

[REDACTED]

[REDACTED]

[REDACTED]

[REDACTED]

[REDACTED]

[REDACTED]

[figure not shown]
[REDACTED]

[REDACTED]

[REDACTED]

[Redacted text block containing approximately 12 lines of obscured content]

[Large redacted text block covering the majority of the page content]

Randomization/Stratification:

Stage 1: Within each cohort, patients will be randomly assigned with respect to the eye, right or left, to receive F1 or F2 (or vehicle for Cohort 1). The contralateral eye will receive vehicle (sham for Cohort 1).

[REDACTED]

[REDACTED]

[REDACTED]

[REDACTED]

[REDACTED]

[REDACTED]

[REDACTED]

Number of Patients:

Stage 1: Stage 1 will have up to 63 patients and approximately 10 cohorts (Cohorts 1 to 6D). The anticipated numbers of patients per cohort are 3 for Cohort 1; 4 for Cohorts 2, 6C, and 6D; and 8 each for Cohorts 3 through 6B.

4.2 Study Objectives and Assessments

The study objective for stage 1 is presented with corresponding assessments in [Table 4-2](#).

[figure not shown]
Table 4-2 Study Objective and Corresponding Assessments - Stage 1

[figure not shown]
Objective	Assessments

To evaluate the safety, exploratory efficacy, and pharmacokinetics of F1 and F2 administered as a [REDACTED] in patients with moderate to severe dry eye disease.
	
Safety Assessments
 
 • AEs • BCVA (manifest refraction at screening and exit visits) • Macroscopic hyperemia assessment and slit-lamp biomicroscopy • Dilated ophthalmic exam • Photographic conjunctival hyperemia assessment • IOP • Vital signs • Laboratory tests (chemistry, hematology, urinalysis) • Urine pregnancy test (for females of childbearing potential) 
Pharmacokinetic Assessments
 
 • PK assessments will be detailed in a separate PK analysis plan. 
[REDACTED]
 
 • [REDACTED] • [REDACTED] • [REDACTED] • [REDACTED] • [REDACTED] • [REDACTED] • [REDACTED] • [REDACTED] 
[REDACTED]
 
 • [REDACTED]

[figure not shown]
AE = adverse event; BCVA = best-corrected visual acuity; F1 [REDACTED] F2 = [REDACTED] IOP = intraocular pressure; OSDI = Ocular Surface Disease Index; PK = pharmacokinetic; TBUT = tear film break-up time; VAS = visual analog scale

[figure not shown]
4.3 Schedule of Activities

The schedule of activities is presented in [Table 4-3](#) (stage 1) and [Table 4-4](#) (stage 2). If retreatment is given at Week 12, the stage 1 retreatment schedule will be following the stage 2 retreatment schedule (see post-retreatment follow-up visits in [Table 4-4](#)).

5. Statistical Methodology and Study Endpoints

5.1 Statistical Methods Planned in the Protocol and Determination of Sample Size

This SAP for stage 1 will be approved prior to final database lock. The SAP expands the statistical section of the protocol and contains a detailed description of methods to analyze data collected in the study. The text portion of the SAP will be included in the clinical study report report as Appendix 16.1.9. Information on the PK analyses can be found in the PK data analysis plan, which is a separate document.

5.1.1 Statistical and Analytical Plans

5.1.1.1 Common Conventions

5.1.1.1.1 Analysis Populations

The analysis populations will consist of patients as defined in [Table 5-1](#).

Table 5-1 Analysis Populations – Stage 1

Population	Definition	Study Treatment
Safety	All patients who are treated	Actual received ^a
Modified intent-to-treat (mITT)	All randomized patients who have baseline and at least 1 postbaseline assessment for 1 or more of the exploratory efficacy measurements	Randomized assignment

^a Patients will be summarized according to the first study treatment received or study treatment received for majority of treatment period.

5.1.1.1.2 Study Treatments

The following treatment groups and cohorts are defined for stage 1 in this study:

Cohort	Treatment Group
Cohort 5A	RESTASIS X F1
Cohort 4	RESTASIS X F1
Cohort 6C	RESTASIS X F1 with retreatment at week 12
Cohort 3	RESTASIS X F1
Cohort 2	RESTASIS X F1
Cohort 6B	RESTASIS X F2
Cohort 6D	RESTASIS X F2 with retreatment at week 12
Cohort 6A	RESTASIS X F2
Cohort 1	Vehicle

Data will be analyzed by treatment group/cohort, unless otherwise specified.

5.1.1.1.3 Statistical Methodology

The methodologies defined in Table 5-2 apply as specified to individual endpoints defined in this SAP for stage 1.

Table 5-2 Statistical Methodology – Stage 1

Methodology	Description
Categorical counts	
 • Number of patients in individual categories 
 ○ Patients with ≥ 1 qualifying event counted once per individual category
Categorical descriptives	
 • Number and percentage of patients in individual categories 
 ○ Patients with ≥ 1 qualifying event counted once per individual category • N1 if percentage denominator \neq number of patients in the population (standard percentage denominator) 
 ○ N1 = patients with nonmissing value
Continuous descriptives	
 • N1, mean, SD, median, minimum, maximum • N1 = patients with nonmissing value
CFB descriptives	
 • Continuous descriptives for baseline, postbaseline, and CFB values • N1 = patients with nonmissing values at both baseline and the specified postbaseline analysis visit
Responder	
 • Categorical descriptives for responders and nonresponders • N1 = patients with nonmissing values at both baseline and the specified postbaseline analysis visit

CFB = change from baseline

Two treatment cycles are defined in this analysis plan. Treatment Cycle 1 includes all visits from study baseline (also called cycle 1 baseline) to Week 24 or Exit visit if a patient receives ██████████ throughout the study, or to the last visit before retreatment if a patient receives ██████████ during the study. For visits in treatment Cycle 1, refer to study windows in Section 6.2. Treatment Cycle 2 applies to patients who receive retreatment, and includes all visits from retreatment and thereafter. Visits in treatment Cycle 2 will be determined based on the study days relative to the retreatment visit using the study windows specified in Section 6.2.

The study baseline value of an assessment will be the measurement prior to the treatment at Day 1 unless it is missing. In that case, the last nonmissing value recorded prior to the treatment (Day 1) will be used instead. The cycle baseline (also called cycle 2 baseline) value of an assessment will be the measurement prior to the retreatment at Week 12 from the first treatment unless it is missing. In that case, the last nonmissing value recorded prior to the retreatment (Week 12) will be used instead.

Ocular evaluation will be summarized by study eye and contralateral eye separately.

Some raw and derived data listings will be provided, and will be fully defined in the table, figure, and data listing specification document.

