5.1.1.1.4 Missing Data

General missing data handling conventions are summarized as follows:

- Missing data will not be imputed and all analyses will be based on observed data.
- Partial dates handling conventions are specified in Section 6.3, but will be listed in the data listings as they appear on the electronic case report forms (eCRFs).

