5.1.1.3.5 Patient Symptoms (Visual Analog Scale)

A short questionnaire utilizing a VAS to quantify the severity of symptoms of dry eye will be administered. The questions refer to TODAY only including overall ocular discomfort from dry eye disease, level of discomfort experienced from symptoms as specified in [Table 6-18](#). The score will be 0 to 100 with 0 = none and 100 = extreme.

Patient symptoms (VAS) will be summarized by treatment group as shown in [Table 5-13](#).

Table 5-13 Patient Symptoms (Visual Analog Scale) Summaries

Endpoint	Description	Timing	Methodology
Overall VAS score ^a	Summary by analysis visit	Cycle 1: Study baseline (Day 1) and Weeks 12 and 24 Cycle 2: Cycle baseline and Weeks 8R and 12R	CFB descriptives
Worse VAS score ^a	Summary by analysis visit 
 For each patient, the symptom among all 9 symptoms (specified in Table 6-18) with the worst VAS at baseline (Day 1) will be used. If no single symptom can be identified at baseline (Day 1), the symptom with the worst VAS score at screening will be used. 	Cycle 1: Study baseline (Day 1) and Weeks 12 and 24 Cycle 2: Cycle baseline and Weeks 8R and 12R	CFB descriptives

^a All patient symptoms (VAS) data will be listed.

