5.1.1.4.3 Clinical Laboratory Assessments

Clinical laboratory assessments will be summarized by treatment group for the safety population as shown in [Table 5-19](#).

Table 5-19 Clinical Laboratory Summaries

Endpoint	Description	Timing	Methodology
Descriptives	Summary by laboratory category, parameter and analysis visit 
 Parameters specified in Table 6-22 	Cycle 1: Study baseline (screening), Week 12 (for Cohorts 6C and 6D only), and Week 24 Cycle 2: Cycle baseline and Week 12R	CFB descriptives

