5.1.1.4.5.5 Photographic Conjunctival Hyperemia

The photographic conjunctival hyperemia grading consists of global assessments and regional assessments, which will be done using a Canfield camera in each eye at the scheduled visits. Global assessment includes global, global nasal and global temporal assessment, and regional assessment includes superior temporal, superior nasal, inferior temporal, and inferior nasal assessment. It will be graded as 0 = none, +0.5 = trace, +1 = mild, +2 = moderate, +3 = severe, CG = cannot grade, and NE = not evaluated.

Photographic conjunctival hyperemia will be summarized by treatment group for the safety population as shown in [Table 5-25](#).

Table 5-25 Photographic Conjunctival Hyperemia Summaries

Endpoint	Description	Timing	Methodology
Global assessment: severity grade	Summary by analysis visit	Cycle 1: Study baseline (Day 1), Day 2, and Weeks 1, 2, 4, 8, 12, and 24 Cycle 2: Cycle baseline, Day 1R, and Weeks 1R, 4R, 8R, and 12R	Categorical descriptives

5.1.1.4.5.6 Intraocular Pressure

Measurement of intraocular pressure (IOP) will be taken for each eye using the Goldmann applanation tonometer affixed to a slit lamp at the scheduled visits.

IOP will be summarized by treatment group for the safety population as shown in [Table 5-26](#).

Table 5-26 Intraocular Pressure Summaries

Endpoint	Description	Timing	Methodology
IOP ^a	Summary by analysis visit	Cycle 1: Study baseline (Day 1), Week 12 (for Cohorts 6C and 6D only), and Week 24 Cycle 2: Cycle baseline, Week 12R	CFB descriptives

IOP = intraocular pressure

^a All IOP data will be listed.

5.1.1.4.5.7 REFRESH PLUS Use

REFRESH PLUS use will be summarized by treatment group for the safety population as shown in [Table 5-27](#).

Table 5-27 REFRESH PLUS Use and Compliance Summaries

Endpoint	Description	Timing	Methodology
REFRESH PLUS descriptives	Summary by analysis visit	Cycle 1: Study baseline (Day 1), Day 2, and Weeks 1, 2, 4, 8, 12, and 24 Cycle 2: Cycle baseline, Day 1R, and Weeks 1R, 4R, 8R, and 12R	CFB descriptives

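### The cycle 2 baseline may fall back to a value taken before any study drug; for VAS, IOP and laboratory tests it would do so if a retreated patient's Week 12 value is missing

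*SAP*

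**What the plan says.** SAP 5.1.1.1.3 defines two treatment cycles, each with its own baseline.

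- **Study (cycle 1) baseline:** "The study baseline value of an assessment will be the measurement prior to the treatment at Day 1 unless it is missing". If it is missing, the latest nonmissing earlier value is used.
- **Cycle 2 baseline:** the "value of an assessment will be the measurement prior to the retreatment at Week 12 from the first treatment unless it is missing". If it is missing, "In that case, the last nonmissing value recorded prior to the retreatment (Week 12) will be used instead".

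The timing columns for three measures matter here:

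- **VAS** (Table 5-13): "Cycle 1: Study baseline (Day 1) and Weeks 12 and 24 Cycle 2: Cycle baseline and Weeks 8R and 12R"
- **IOP** (Table 5-26): "Cycle 1: Study baseline (Day 1), Week 12 (for Cohorts 6C and 6D only), and Week 24", then cycle baseline and Week 12R in Cycle 2
- **Laboratory tests** (Table 5-19): "Cycle 1: Study baseline (screening), Week 12 (for Cohorts 6C and 6D only), and Week 24", then cycle baseline and Week 12R in Cycle 2

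All three are summarised with change-from-baseline descriptives. Table 5-2 counts in N1 every patient with a nonmissing baseline and a nonmissing value at the visit concerned. Retreatment in Stage 1 is planned for Cohorts 6C and 6D (Protocol 5.10), with 4 patients each (SAP 5.1.2).

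**The concern.** The two fallback sentences have the same form but not the same effect. For the study baseline the fallback is safe on this score, because every value before the first treatment precedes study drug. For cycle 2, the period before retreatment includes the time before the first treatment as well as the 12 weeks after it. The rule does not separate the two.

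Where a measure has no value between the pre-drug baseline and Week 12, one pre-drug measurement would serve as baseline for both cycles. The Cycle 2 row is there to show what follows the second treatment, yet for that patient it would span both treatments. It would then be averaged with changes that start at Week 12. Cohorts 6C and 6D are the only planned source of retreatment data in Stage 1, IOP and laboratory tests are safety measures, and SAP 5.1.1.7 says the analyses are to inform the design of later studies.

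**Working it through.** **Inputs.** The planned cohort sizes in SAP 5.1.2 reproduce the stated maximum: 3 (Cohort 1) + 3 × 4 (Cohorts 2, 6C, 6D) + 6 × 8 (Cohorts 3, 4, 5A, 5B, 6A, 6B) = 63. So n = 4 in each retreated cohort, 8 patients in all. The documents give no effect size, SD or missing rate for these measures. The changes and rates used below are assumptions.

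**Step 1: where the fallback lands.** Remove Week 12 from each measure's Cycle 1 timing and take the latest remaining time before retreatment.

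| Measure | Listed before Week 12 | Fallback | After first treatment? |
|---|---|---|---|
| VAS | Day 1 | Day 1 | No |
| IOP | Day 1 | Day 1 | No |
| Laboratory tests | screening | screening | No |
| Vital signs | baseline, Weeks 1, 8 | Week 8 | Yes |
| Schirmer, TBUT, staining | Day 1, Weeks 4, 8 | Week 8 | Yes |
| OSDI | Day 1, Week 4 | Week 4 | Yes |

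Table 6-8 also provides for endpoints seen only at Day 1, Week 12 and Week 24.

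**Step 2: effect on a patient.** Let d1 be the change from the pre-drug value to Week 12, and d2 the change from Week 12 to the Cycle 2 visit. The intended Cycle 2 change is d2. With a pre-drug baseline it becomes d1 + d2.

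**Step 3: effect on the cohort mean.** With m of 4 patients on the pre-drug fallback, and common d1 and d2,

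mean = [(4 − m) × d2 + m × (d1 + d2)] / 4 = d2 + (m/4) × d1.

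With d2 = 0:

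| Assumed d1 | m = 1 | m = 2 |
|---|---|---|
| VAS −10 | −2.5 | −5 |
| VAS −20 | −5 | −10 |
| IOP +4 mm Hg | +1 mm Hg | +2 mm Hg |

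**Step 4: what the row shows.** For changes of (−20, 0, 0, 0), the mean is −5. The squared deviations are 225 + 25 + 25 + 25 = 300, so SD = √(300/3) = 10. The median is 0, the minimum −20 and the maximum 0. N1 is 4 in the Cycle 2 row. In the Cycle 1 Week 12 row it is 3, because that patient has no Week 12 value.

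**Step 5: how often.** If each of the 8 patients is retreated and independently lacks the Week 12 value of a given measure with probability p, the chance of at least one case is 1 − (1 − p)^8. That is 15%, 34% and 57% for assumed p of 2%, 5% and 10%.

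**The case against.** The strongest reply is that the rule may never operate. Retreatment follows an investigator's decision at Week 12, so the patient is in the clinic, where VAS and IOP are taken. A lost or unusable central-laboratory sample is the easier case to imagine. The visit procedures in Protocol 8.4 are redacted, so it cannot be said whether a sample could be redrawn before the second dose. This stands, and it limits the weight of the point.

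A reader might infer that the mixture would be invisible. The documents do not support that. The Cycle 2 row carries no flag, but the lower N1 in the Cycle 1 Week 12 row, the minimum and maximum, and the listings (SAP 6.2 puts all assessments in them) would let a careful reader trace it among four patients.

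A reader might also see a contradiction with SAP 5.1.1.1.4, which says "Missing data will not be imputed and all analyses will be based on observed data". That goes too far. The section sets general conventions, and the fallback is a specific rule that selects a value actually observed, as the study baseline rule does.

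It could be argued that Tables 6-10 to 6-15 already confine the cycle baseline to Retreatment Day 1. They are not stated to override the fallback. The SAP does not treat baseline windows as that strict elsewhere either: the Cycle 1 window tables that list a study baseline put it at Treatment Day 1, yet Table 5-19 takes the laboratory baseline from screening.

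**Conclusion.** Wrong as written, minor severity. Followed literally, the rule makes a pre-drug value the retreatment baseline for VAS, IOP or laboratory tests when a retreated patient has no Week 12 value and no unscheduled one after the first treatment. Each such patient shifts the Cycle 2 mean of a four-patient cohort by a quarter of that patient's first-treatment change.

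It would be too strong to say that first-treatment change alone is reported as retreatment change: the affected figure is the sum of the two. Nor is any error rate or power at stake, since Stage 1 is descriptive with an empirically chosen sample size.

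The conclusion rests on three readings. The schedule-of-activities tables are not visible, so the timing comes from the SAP summary tables. Cycle 2 change is taken from the cycle baseline, which the timing columns imply but no sentence states. Retreatment follows the plan, with 4 patients in each of 6C and 6D.

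**What to change.** Replace the cycle 2 fallback in SAP 5.1.1.1.3 with wording to this effect:

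*If the Week 12 pre-retreatment value is missing, the latest nonmissing value obtained after the first treatment and before retreatment is used. If there is none, the cycle 2 baseline is missing and the patient is left out of N1 in the Cycle 2 change-from-baseline row.*

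In the examples above, the (m/4) × d1 term disappears and the row reports d2 in the remaining patients.

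No recency limit should be added. A cut-off at Treatment Day 42, where the Week 8 window starts in Tables 6-2 and 6-3, would discard usable post-treatment values. For vital signs the Week 8 window starts at Day 32 (Table 6-4). OSDI has no Week 8 visit, and its Week 4 visit is targeted at Day 28 (Table 6-6).

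The cost is one SAP sentence and one programming condition, with no new data. N1 falls from 4 to 3 in a row with one affected patient. That patient's values stay in the listings.

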5.1.1.3 Exploratory Efficacy Analyses

5.1.1.3.1 Schirmer's Tear Test (With Anesthesia)

Schirmer's tear test (with anesthesia) will be summarized by treatment group as shown in [Table 5-9](#).

Table 5-9 Schirmer's Tear Test Summaries

Endpoint	Description	Timing	Methodology
Schirmer's tear test score ^a	Summary by analysis visit	Cycle 1: Study baseline (Day 1) and Weeks 4, 8, 12, and 24 Cycle 2: Cycle baseline and Weeks 4R, 8R, and 12R	CFB descriptives
Number (percent) of responders	Summary by analysis visit 
 Responder defined as ≥ 10 mm/5 min increase from study baseline in Schirmer's tear test score 	Cycle 1: Weeks 4, 8, 12, and 24	Categorical descriptives

^a All schirmer's tear test data will be listed.

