5.1.1.3.7 Treatment Assessment by Investigator

The follow-up investigator will complete a global evaluation of the overall effect of investigational medication administered in reference to the Baseline visit (Day 1) prior to the [REDACTED] of the investigational medication for each eye at the scheduled visits. The global evaluation score will be assessed based on the following scale:

- 0 = Completely cleared, no sign or symptom of disease
- 1 = Almost cleared: very significant clearance in disease with only traces of active disease remaining (approximately 90% improvement)
- 2 = Marked response: significant improvement with some disease remaining (approximately 75% improvement)
- 3 = Moderate response: intermediate improvement, between slight and marked (approximately 50% improvement)
- 4 = Slight response: some improvement in disease state but significant disease remains (approximately 25% improvement)
- 5 = Condition unchanged
- 6 = Condition worsened

Treatment assessment by investigator will be summarized by treatment group as shown in [Table 5-15](#).

Table 5-15 Treatment Assessment by Investigator Summaries

Endpoint	Description	Timing	Methodology
Global evaluation score	Summary by analysis visit for the raw score	Cycle 1: Weeks 8, 12, and 24 Cycle 2: Week 8R, and Week 12R	Continuous descriptives

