5.1.1.4.5 Other Safety Analyses

5.1.1.4.5.1 Best-Corrected Visual Acuity

Manifest refraction will be performed at screening and used for BCVA at all subsequent visits until study exit. If there is a decrease in BCVA, the manifest refraction should be repeated as confirmation. Visual acuity (in Snellen equivalents) will be measured for each eye using a logarithmic visual acuity chart for testing at 10 feet (3 meters) at the scheduled visits.

The visual acuity will be recorded on the eCRF in Snellen equivalent units (eg, 20/63) as the lowest line read with 1 or 0 mistakes.

The line CFB at each evaluation is calculated using the following algorithm:

line change = (10)*[log₁₀ (XB/20) - log₁₀ (XF/20)], where

- XB = denominator of the Snellen equivalent unit at baseline
- XF = denominator of the Snellen equivalent unit at post treatment visit

Each logarithmic value is to be rounded to the nearest tenth before subtraction. A positive value indicates an improvement and a negative value indicates a worsening. For example, the line change for a Snellen equivalent unit of 20/25 at baseline followed by a Snellen equivalent unit of 20/80 at day 2 would be

$$\text{Line change} = 10 \times [\log_{10}(25/20) - \log_{10}(80/20)] = 10 \times (0.1 - 0.6) = -5$$

which represents a worsening of 5 lines in visual acuity.

BCVA will be summarized by treatment group for the safety population as shown in [Table 5-21](#).

Table 5-21 BCVA Summaries

Endpoint	Description	Timing	Methodology
Line CFB ^a	Summary by analysis visit and line change categories defined below or line change of ≤ -2 , -1 , 0 , $+1$, or $\geq +2$: 
 • Better (line changes of $\geq +2$) • No change (line changes of -1, 0, $+1$) 
 ○ Line change of $+1$ ○ Line change of 0 ○ Line change of -1 • Worse (line changes of ≤ -2) 	Cycle 1: Day 2 and Weeks 1, 2, 4, 8, 12, and 24 Cycle 2: Day 1R and Weeks 1R, 4R, 8R, and 12R	Categorical descriptives

CFB = change from baseline

^a All BCVA will be listed.

5.1.1.4.5.2 Macroscopic Bulbar Hyperemia

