5.1.1.7 Interim Analyses

An interim database lock of stage 1 will not be conducted until after all patients in Cohorts 1 through 6B complete the study and all patients in Cohorts 6C and 6D complete at least Week 1 following retreatment. Statistical analyses will be performed following the database lock to support the design of future clinical studies.

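### Stage 1 randomises eyes within patients, but the SAP as supplied plans no between-eye difference, so drug versus vehicle has no paired SD, interval or response pattern

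*SAP*

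**What the plan says.** SAP 4.1 describes stage 1 as "Single-dose, paired-eye comparison, dose escalation, vehicle-controlled". Within each cohort, "patients will be randomly assigned with respect to the eye, right or left, to receive F1 or F2". The other eye of the same patient receives vehicle. In cohort 1 the pair is vehicle and sham. Protocol 5.4 gives the same allocation.

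For analysis, SAP 5.1.1.1.3 says: "Ocular evaluation will be summarized by study eye and contralateral eye separately". Table 5-2 lists the available methods:
- counts and percentages;
- N1, mean, SD, median, minimum and maximum;
- change from baseline, described as "Continuous descriptives for baseline, postbaseline, and CFB values";
- responder counts.

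The readable ocular tables draw only on these methods. Examples are the Schirmer responder ("Responder defined as ≥ 10 mm/5 min increase from study baseline"), the investigator's global score ("Summary by analysis visit for the raw score") and the BCVA category "Worse (line changes of ≤ -2").

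SAP 5.1.2 says the sample size is empirical. SAP 5.1.1.7 gives the purpose of the analyses: "Statistical analyses will be performed following the database lock to support the design of future clinical studies".

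**The concern.** In cohorts 2 to 6D the fellow vehicle eye is the only concurrent randomised control. The quantity that the randomisation makes available is the within-patient difference between eyes, and the readable SAP never defines it.

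A reader of two separate eye rows can subtract the means but has no measure of how variable that difference is. Judging it from the two per-eye SDs ignores the pairing. For binary outcomes, the separate counts do not show whether the same patients responded in both eyes.

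The point estimate is not safe in every case either. Missing data are not imputed (SAP 5.1.1.1.4), and nothing restricts the two rows to patients with both eyes observed, so a subtraction may mix different patients.

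The stated aim is to support later designs. The SD of the paired difference, or equivalently the between-eye correlation, is what a later paired-eye study would need, and the planned summaries supply neither.

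**Working it through.** **Inputs from the documents.** SAP 5.1.2 plans 3 patients in cohort 1, 4 in each of cohorts 2, 6C and 6D, and 8 in each of cohorts 3, 4, 5A, 5B, 6A and 6B.

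**Plan's own figure.** 3 + 3 × 4 + 6 × 8 = 63 patients in 10 cohorts, which matches the SAP. There is no power calculation to reproduce.

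**Assumptions.** The per-eye SD is the same in both eyes and is the unit below. The between-eye correlation ρ is not in the documents, so a range is shown.

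**Step 1: SD of the difference.** SD of difference = √(2(1 − ρ)) per-eye SD. For ρ = 0, 0.5, 0.7 and 0.8 this is 1.41, 1.00, 0.77 and 0.63. Over every possible ρ (1 to −1) it runs from 0 to 2, so the two per-eye SDs alone do not fix it.

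**Step 2: 95% half-widths.**
- Paired: t(0.975, n − 1) × √(2(1 − ρ)/n)
- Ignoring pairing: t(0.975, 2n − 2) × √(2/n)

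For n = 8 and ρ = 0.5: 2.365 × √(1/8) = 0.84. Ignoring pairing: 2.145 × √(2/8) = 1.07.

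| n | ρ = 0 | ρ = 0.5 | ρ = 0.7 | ρ = 0.8 | Ignoring pairing |
|---|---|---|---|---|---|
| 8 | 1.18 | 0.84 | 0.65 | 0.53 | 1.07 |
| 4 | 2.25 | 1.59 | 1.23 | 1.01 | 1.73 |
| 3 | 3.51 | 2.48 | 1.92 | 1.57 | 2.27 |

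The SAP plans neither interval. The last column is only a yardstick.

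**Step 3: when pairing narrows the interval.** The two half-widths are equal at ρ = 1 − [t(0.975, 2n − 2)/t(0.975, n − 1)]². This gives 0.18 (n = 8), 0.41 (n = 4) and 0.58 (n = 3). Below these values the paired interval is wider, but it is still the one that matches the randomisation.

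**Step 4: same summaries, different pairing (constructed example, n = 8).** Let the study-eye changes be 0, 1, …, 7 and the contralateral changes −2, −1, …, 5. Each eye has SD 2.45 and the mean difference is 2.0. Paired in the same order, the SD of the difference is 0. Paired in reverse order, it is 4.90, with a 95% half-width of 4.1. The separate-eye summaries are identical in both cases.

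**Step 5: responders (constructed example, n = 8).** Suppose 3/8 study eyes and 1/8 contralateral eyes respond. Written as both / study eye only / contralateral only / neither, this fits 0/3/1/4 and also 1/2/0/5. The planned counts cannot tell them apart.

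**The case against.** The strongest objection is that not everything can be read. The text of protocol 7.3.2 on exploratory efficacy is blacked out, parts of SAP 4.1 are redacted, and the table specifications are a separate document. A paired summary may exist there. This stands as a limit on scope. However, SAP 5.1 says the SAP holds the detailed methods, so a paired method belongs in Table 5-2.

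Second, cohorts are small and listings carry the pairing. Schirmer, BCVA and IOP are explicitly listed, and SAP 6.2 says all assessments go into their listings. With 8 patients, a both-or-neither pattern can be read off by hand. This too stands: the data are not lost. A hand calculation is still not a planned summary.

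Third, the stage is descriptive and empirically sized, and the protocol promises only general descriptive statistics, which the SAP delivers. That is why the point is an improvement and not an error.

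Fourth, intervals at every visit add up. Count change from baseline in Schirmer, TBUT, corneal staining and total conjunctival staining, plus IOP, for the eight active cohorts listed in SAP 5.1.1.1.2. Each of the first four measures has 6 × 4 + 2 × 3 + 2 × 3 = 36 cohort-visits and IOP has 6 + 4 = 10, so there are 4 × 36 + 10 = 154 intervals. Many would be wide: at n = 4 the half-width is still 1.01 SD when ρ = 0.8. This is a reason to trim the intervals and label them as descriptive. It does not remove the case for the paired SD.

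Finally, slit-lamp findings and dilated-examination grade increases are also eye-level safety outcomes, and a paired summary should not be confined to efficacy. That is fair, and the fix can be extended to them.

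**Conclusion.** The point holds for the SAP as supplied. Stage 1 is a paired-eye randomised comparison, and its planned ocular summaries are per eye only. An SD is given for each eye, but none for the difference between eyes, and there is no interval or cross-classification of response.

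The point estimate is recoverable when both rows contain the same patients, and time trends common to both eyes then cancel. Its precision is not recoverable: for ρ between 0 and 0.8, the paired 95% half-width in a cohort of 8 ranges from 1.18 to 0.53 per-eye SD, a factor of about 2.2. These figures rest on equal per-eye SDs and on assumed correlations.

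No planned test is affected. The gap concerns estimation, and how well stage 1 serves the design of later studies.

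**What to change.** Add a descriptive paired-eye method to Table 5-2, limited to patients with both eyes observed at the visit (and at baseline for change scores), by cohort, cycle and visit:

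1. **Schirmer, TBUT, corneal and conjunctival staining, IOP:** study eye minus contralateral eye in change from baseline, with N, mean, SD, median, minimum, maximum and a 95% t interval on the paired differences.
2. **Investigator global score and the eye-specific treatment-satisfaction item:** paired difference in the raw score. The global score is already rated against baseline.
3. **Schirmer responders and the SAP's own worsening category for BCVA:** counts of both eyes, study eye only, contralateral eye only and neither.
4. **Macroscopic and photographic global hyperemia:** full cross-tabulation of study-eye by contralateral-eye grade, so no cut-off is needed.

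Show cohort 1 separately as vehicle versus sham, with individual differences and no interval, because n = 3. Label all intervals as descriptive and unadjusted. If output volume is a concern, keep the SD of the difference throughout and give intervals only at a few visits named in advance. The four-way count in item 3 can also be used for slit-lamp and dilated-examination grade increases.

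The cost is SAP wording and extra blocks in the ocular tables, with no new data, patients or procedures. The drawback is many wide intervals at n = 4 to 8. If the separate table specifications already contain these summaries, a sentence in the SAP saying so is enough.
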